#### **11.13.9. Sub-study Amendment Pharmacokinetics**

Pharmacokinetic analysis will be the responsibility of the Clinical Pharmacology

Modeling & Simulation Department (CPMS), GSK. Individual Plasma CAB and RPV concentration-time data will be analyzed by non-compartmental methods with WinNonlin 5.2 or higher. Calculations will be based on the actual sampling times recorded during the study. PK intervals are defined for each arm of the substudy in [Table 16](#), and the concentration at the end of the interval will also serve as the predose concentration for the subsequent interval. The following pharmacokinetic parameters will be determined for each interval, as data permit: maximum concentration ( $C_{max}$ ), time to  $C_{max}$  ( $t_{max}$ ), area under the plasma concentration-time curve through the end of the dosing interval ( $AUC(0-\square)$ ), and concentration at the end of the dosing interval ( $C_{\square}$ ).

Plasma concentration data will be summarized descriptively by analyte and treatment regimen and presented in graphical and/or tabular form. Parameters will be summarized by analyte and treatment regimen.  $C_{max}$ ,  $AUC(0-\square)$  and  $C_{\square}$  treatment comparisons are described above (see [Table 15](#));  $t_{max}$  will not be compared statistically. All pharmacokinetic data (both CAB and RPV) will be stored in the Archives, GlaxoSmithKline Pharmaceuticals, R&D. Additional analyses including modelling, simulation and external validation may be performed to assist in the clinical interpretation of these data and will be reported separately.

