PK sample collection j												
Pre dose PK sampling	X		X		X	X	X		X			
2h Post dose PK sampling			X		X	X	X					
Post dose PK sampling (~Cmax)		X		X				X		X		
PROs l												
HIVTSQc									X k			
HIVTSQs			X						X k		X	
NRSh	X	X	X	X			X	X	X	X		
Preference Thigh inj. vs Gluteal inj.							X				X	

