#### **Preference Questionnaire**

A preference question was used to assess patients’ preference, and reasons for preference, for the thigh injections compared with the gluteal injections. The “Preference” questionnaire will include a single item questions evaluating preference of HIV treatment and the attributes supporting this preference.

**11.13.5.4. Sub-study: Pharmacokinetics sample collection****Table 14 Sub-study CAB and RPV Plasma Pharmacokinetic Sample Schedule**

Group	Analytes	Sample Times Relative to Dose
Participants receiving CAB LA + RPV LA Q4W injections	CAB and RPV	Pre-Dose: Screening (Week -4), Day 1, Week 4, Week 8, Week 12, Week 16 2 hours Post dose: Day 1, Week 4, Week 8, Week 12 1 Week Post dose: Week -3, Week 1, Week 13
Participants receiving CAB LA + RPV LA Q8W injections	CAB and RPV	Pre-Dose: Screening (Week -8), Day 1, Week 8, Week 16 2 hours Post dose: Day 1, Week 8 1 Week Post dose: Week -7, Week 1, Week 9 4 Week Post dose: Week -4, Week 4, Week 12

**PK window collection:** All scheduled PK samples should be collected on the Day of the corresponding visit. Pre-dose samples will be taken prior to performing dosing within the clinic.

Additional details concerning handling of PK samples, labeling and shipping directions will be supplied in the central laboratory manual.

**11.13.6. Sub-study Amendment: Study Treatment****11.13.6.1. Sub-study Amendment: Investigational Product and Other Study treatment**

Please refer to Sections [6.1.1.3](#) Cabotegravir Injectable Suspension (CAB LA) and Section [6.1.1.4](#) Rilpivirine Injectable Suspension (RPV LA) of main A2M protocol.

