#### **11.13.8.2. Sample Size Considerations**

No formal sample size calculation has been made. The sample size of 41 subjects per treatment arm (Q8W, Q4W) is sufficient to evaluate the geometric mean ratio (thigh injection vs gluteal injection) of PK parameters and to assess the safety parameters within 16 weeks of the thigh injection phase.

PK parameter comparisons of interest are shown in [Table 15](#). Each comparison (first or last thigh injection vs gluteal injection) will be evaluated separately by treatment arm and analyte (CAB, RPV). In the main study, the observed between subject coefficient of variation (CVb) for Week 96 trough PK concentrations among overall population ranges from 40% to 56%. Conservatively, assuming within subject coefficient of variation is 56%, it is estimated that the half width of the 90% confidence interval for the geometric mean ratios on log-scale will be within 19%. If the point estimate of the ratio of geometric means is 1, then the 90% confidence interval will be approximately (0.83, 1.21) on the original scale.

**Table 15** Planned Pharmacokinetic Parameter Comparisons between Thigh and Gluteal Injections

Parameters (CAB and RPV)	Q8W	Q4W
$C_{max}$ , $C_{tau}$ (end of dosing interval a ), AUC(0-tau)	Thigh Injection 1: Gluteal Injection	Thigh Injection 1: Gluteal Injection
	Thigh Injection 2: Gluteal Injection	Thigh Injection 4: Gluteal Injection

aDosing interval is defined in Table 16.

**Table 16** Dosing Intervals for Each Treatment Arm

Treatment Arm	Dosing Interval		
	Gluteal Injection	First Thigh Injection	Last Thigh Injection
Q8W	Week -8 to Day 1	Day 1 to Week 8	Week 8 to Week 16
Q4W	Week -4 to Day 1	Day 1 to Week 4	Week 12 to Week 16

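### Thigh sub-study: a 2-hour sample taken only after thigh injections puts the primary Cmax and AUC ratios on unequal sampling, and the protocol gives two definitions of the peak endpoint

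*Protocol*

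**What the plan says.** **Parameters.** Section 11.13.9 sets out the derivation: "The following pharmacokinetic parameters will be determined for each interval, as data permit: maximum concentration". It adds tmax, AUC(0-tau) and Ctau, uses actual sampling times, and has no rule for leaving out or aligning the 2-hour sample. Section 11.13.8.4.1 models log Cmax, Ctau and AUC(0-tau) as the primary thigh:gluteal ratios.

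**Comparisons.** Section 11.13.8.2: "Each comparison (first or last thigh injection vs gluteal injection) will be evaluated separately by treatment arm and analyte". Table 16 defines one gluteal interval per arm: Week -4 to Day 1 for Q4W and Week -8 to Day 1 for Q8W.

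**Sampling.** Table 14 (Section 11.13.5.4) lists the Q4W 2-hour draws as "Day 1, Week 4, Week 8, Week 12", which are the four thigh injections. For Q8W they are Day 1 and Week 8, again thigh only. Sections 11.13.5.1 and 11.13.5.2 agree.

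**Peak endpoint.** Sections 11.13.2 and 11.13.3 name a post-dose concentration, labelled ~Cmax. In both Time and Events tables the row "Post dose PK sampling (~Cmax") is separate from the 2-hour row. That row also marks Week 17, after the first return gluteal injection. Table 14 has no Week 17 draw, and Tables 15 and 16 do not use one.

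**The concern.** A non-compartmental Cmax is the largest value among the samples taken. If one site is sampled more often, its expected maximum is at least as high even when the two true profiles are identical, and a larger sample does not remove the difference. Here the more heavily sampled site is always the thigh. Section 11.13.1 reports that Phase 1 CAB concentrations after thigh injection ran slightly above prediction early on, possibly from faster absorption. A sampling artefact in Cmax points the same way and could be read as confirming that signal. Because the sub-study only estimates ratios, any systematic shift goes directly into the reported result.

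The two descriptions of the peak matter for the same reason. Under one, Cmax is distorted by the extra draw; under the other it is not. A reader cannot tell from the protocol which will be reported.

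**Working it through.** **1. The plan's own precision.** Inputs from Section 11.13.8.2: "The sample size of 41 subjects per treatment arm (Q8W, Q4W) is sufficient to evaluate the geometric mean ratio"; "assuming within subject coefficient of variation is 56"%.
- Within-subject log-SD = sqrt(ln(1 + 0.56²)) = 0.522.
- SE of the log ratio = 0.522 × sqrt(2/41) = 0.1153.
- Half-width = 1.645 × 0.1153 = 0.190, giving exp(±0.190) = 0.83 to 1.21.

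This reproduces the plan's statements that "the half width of the 90% confidence interval for the geometric mean ratios on log-scale will be within 19"% and that "the 90% confidence interval will be approximately (0.83, 1.21) on the original scale".

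**2. Samples per interval** (Tables 14 and 16, counting the end-of-interval trough).

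| Arm | Gluteal reference | First thigh | Last thigh |
|---|---|---|---|
| Q4W | Wk -4 pre-dose, Wk -3, Day 1: **3** | Day 1 pre-dose, 2 h, Wk 1, Wk 4: **4** | Wk 12 pre-dose, 2 h, Wk 13, Wk 16: **4** |
| Q8W | Wk -8 pre-dose, Wk -7, Wk -4, Day 1: **4** | Day 1 pre-dose, 2 h, Wk 1, Wk 4, Wk 8: **5** | Wk 8 pre-dose, 2 h, Wk 9, Wk 12, Wk 16: **5** |

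The thigh times are the gluteal times plus one, so the artefact in an interval maximum can only be zero or upward.

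**3. Size for Cmax, true ratio 1.** The documents give no per-sample variability, peak:trough ratio or 2-hour level. Assumed: log-SD 0.15 to 0.35 per sample, true 2-hour level equal to pre-dose, and a range of peak:trough ratios.

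For a flat profile with independent samples there is a closed form. The expected maximum of 3, 4 and 5 standard normal values is 0.846, 1.029 and 1.163.
- Q4W: exp((1.029 - 0.846) × SD) = exp(0.183 × SD), which is 1.028 at SD 0.15 and 1.066 at SD 0.35.
- Q8W: exp(0.134 × SD), which is 1.020 and 1.048.

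Simulation (400,000 replicates per setting) covers the other Q4W cases:

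| True peak:trough | Samples independent | Pre-dose and 2 h correlated 0.8-0.95 |
|---|---|---|
| 1.0 (flat) | +2.8% to +6.6% | +0.6% to +3.0% |
| 1.2 | +1.2% to +4.9% | +0.3% to +2.3% |
| 1.4 | +0.4% to +3.4% | under +2% |
| 2.0 | 0 to +1.3% | under +1% |

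For Q8W with a flat profile and the same correlations, the tilt is +0.5% to +2.2%. An extreme setting (independent samples, per-sample CV 56%, flat profile) gives exp(0.183 × 0.522) = 1.10 for Q4W.

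**4. AUC.** With the linear trapezoid, inserting a 2-hour point in the 0-168 h segment changes the AUC by 84 × (C2h minus the pre-dose-to-Week-1 line at 2 h). Take Q4W with pre-dose 1, Week 1 at 1.5 and trough 1:
- AUC without the point = 168 × 1.25 + 504 × 1.25 = 840; the line at 2 h is 1 + 0.5 × 2/168 = 1.006.
- C2h = 0.8: 84 × (-0.206) = -17.3, ratio 0.979.
- C2h = 1.0: -0.5, ratio 0.999.
- C2h = 1.5: +41.5, ratio 1.049.

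For Q8W (Week 4 at 1.25) the corresponding ratios are 0.990, 1.000 and 1.025. The sign depends on the 2-hour level, which the documents do not give.

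**5. Week 17.** It lies outside every interval in Table 16 and every comparison in Table 15. Its contribution to the planned ratios is zero whether or not Table 14 lists it.

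**The case against.** **The peak may be the post-dose concentration.** If the 1-week value is the peak, as the endpoint wording suggests, there is no artefact. This is a fair reading, but not the only one. Section 11.13.9 asks for a maximum with its tmax, which implies a search over all samples, and Sections 11.13.8.2 and 11.13.8.4.1 analyse Cmax. In the Q8W table the ~Cmax row also contains the 4-week draws, so that label does not identify one sample either. The conflict is part of the finding.

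**The effect is small and decides nothing.** There is no hypothesis test and no margin. Pre-dose and 2-hour samples from one visit are surely correlated, which roughly halves the tilt or better. An upward Cmax tilt also works against the sub-study's aim of showing similarity, and Ctau, which Section 11.13.2 ties most closely to efficacy, is untouched. All of this stands and limits the weight of the point.

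**It belongs in the analysis plan.** Sample selection for non-compartmental work often does, and that plan is not at hand. But the unequal schedule and the two peak definitions are in the protocol itself.

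**Stronger readings.** A reader might infer that AUC is also tilted toward the thigh; step 4 shows that no direction is established. A reader might infer that dropping Week 17 from Table 14 biases the gluteal reference; it enters no planned ratio. A reader might also want Week 17 as a second gluteal reference, to separate site from calendar time. That sample comes one week after the first gluteal injection following 16 weeks of thigh dosing. Section 11.11.4.1 says both drugs can be detected for 12 months or longer after injections stop, so residual thigh-derived drug is likely. The pre-switch reference follows at least 152 weeks on the regimen, which limits the calendar-time worry.

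**Conclusion.** The point holds as a modest, avoidable defect. If Cmax is the interval maximum, the primary thigh:gluteal Cmax ratio has an artefact that can only be upward: about 0-3% for Q4W under high same-visit correlation and up to about 7% under independence, with somewhat smaller values for Q8W. These figures rest on the assumed log-SDs, peak:trough ratios and correlations, and on no true rise at 2 hours. A real early peak, sampled at one site only, would make the tilt larger.

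Against the stated half-width of about 19% this is minor. That half-width, however, comes from using the top of the observed between-subject range as a conservative within-subject CV. If the within-subject CV were 25% (an assumption), the half-width would be 1.645 × 0.246 × sqrt(2/41) = 0.09, and a shift of a few percent would be more visible.

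AUC rests on unequal time points with unknown direction. Ctau is unaffected. The conflicting peak definitions and the Week 17 mismatch are errors of text that stand regardless of size. The documents do not support a claim that the sub-study's conclusions are at risk.

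**What to change.** - In Sections 11.13.8.4.1 and 11.13.9, state one definition of Cmax and use it in Sections 11.13.2, 11.13.3 and 11.13.8.2 and in the Time and Events row labels.
- Compute the Cmax and AUC(0-tau) used in the primary ratios only from nominal times common to both sites: pre-dose, 1 week, 4 weeks (Q8W only) and end of interval. With matched times, identical profiles give an expected ratio of 1.
- Keep the 2-hour data for description or population PK modelling.
- Reconcile Table 14 with the two Time and Events tables on the Week 17 draw and state what the sample is for. Do not make it a second primary gluteal reference.

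The cost is a few sentences and a table entry, with no new visits or blood draws. Adding a matching 2-hour draw to the gluteal reference interval would also equalise the sampling, but at the price of extra samples.

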## 11.14. Appendix 14: Protocol Amendment History

The Protocol Amendment Summary of Changes Table for the current amendment is located directly before the Table of Contents (TOC).

### Amendment 5 16-Apr-2021

#### Overall Rationale for Amendment 5

The primary purposes of this amendment are:

- To allow participants who become pregnant to remain in the study and not be withdrawn due to pregnancy. Allowing pregnant participants to continue in the study will negate any additional and subsequent fetal exposures to new antiretrovirals agents that would occur if the pregnant participant was withdrawn from the study and placed on an oral SOC regimen. An Appendix, “Information and Guidance for Managing Pregnant Participants” was inserted as Appendix 11, and all subsequent appendices were renumbered accordingly.
- Contraceptive methods have been updated to permit the use of progestogen-only implantable and injectable contraceptives without the requirement of a second highly effective method.
- Removal of the optional collection of cord blood and/or breast milk after delivery.
- Removal of the option for study treatment rechallenge following suspected drug-induced liver injury (DILI)
- Clarification of which participants enter the LTFU phase when CAB+RPV LA marketed product is locally available.
- Clarification added: The Reason for Oral Bridging and Preference questionnaire will also be administered at Withdrawal if it occurred at or before Week 152 only to participants who received oral bridging during the Maintenance and/or Extension Phases.
- Medical Device reporting requirement added
- Co-enrolment (Only applicable for South African participants)
- Clinical and safety references updated
- Removal of the reference to “randomized study treatment” in Overall design sections for alignment with CAB program studies and transition to marketed product plan.

Other additional edits were made, for clarity and/or correction.

Section # and Name	Description of Change	Brief Rationale
Section 1.3 Overall Design	New text added to clarify the Long Term Follow up phase requirements depending on the local availability of marketed product and the reason for stopping the study treatment.	Transition to marketed product
Section 1.4.3 Extension Phase		
Section 1.4.4. Long Term Follow- Up Phase		

Section # and Name	Description of Change	Brief Rationale

Section 4.2.3 Extension phase
 
Section 4.2.4 LTFU Phase- IM Regimen Only
 
Section 5.5. Withdrawal/Stopping Criteria
		

Section 2, Section 4 and Section 7
	
Safety update text added throughout the following sections:
 
 
• Section 2.3.1, Drug Induced Liver Injury (DILI), updated text "All participants with suspected DILI identified in clinical studies to date were receiving oral cabotegravir "
 
• Section 2.3.1 Risk Assessment RPV LA, Risk of treatment failures updated text: "Both IM CAB and RPV have demonstrated antiviral activity in large clinical studies and the two drug combination dosed Q4W has demonstrated sustained antiviral activity in studies 200056, 201584 and 201585 however the efficacy of Q8W dosing remains under evaluation."
 
• Section 2.3.1.1 Other Clinically Relevant Information, Adverse Events of Special Interest, Seizure, updated text: "Several cases of seizure have occurred during the cabotegravir program. These cases have had alternative explanations for their occurrence (...) Several cases of seizure have occurred during the cabotegravir program. These cases have had alternative explanations for their occurrence (...) Report any cases of seizure or seizure like events immediately."
 
• Section 2.3.2 Benefit Assessment, updated text "The antiviral activity against HIV-1 of CAB has been well established through Phase 2 and Phase 3"
 
• Section 4.4 Scientific Rationale for Study Design, updated text "The CAB LA + RPV LA Q4W regimen is currently under evaluation in the ongoing Phase 3 201584 and 201585 studies"
 
• Section 4.5.1 Oral Lead-In Phase, updated the status of study . LAI116482 (LATTE) Phase IIb
 
• Section 7.4.3.4 Prompt Reporting of Serious Adverse Events and Other Events, updated text "Contacts for SAE receipt can be found at the beginning of this protocol on the Sponsor/Medical Monitor Contact
 
	
General safety updates

Section # and Name	Description of Change	Brief Rationale
	
Information page in the Study Reference Manual."
 
 
Section 7.4.5.4 Seizures, updated text: "Several cases of seizure have occurred during the cabotegravir program. These cases have had alternative explanations for their occurrence."
 
	

Section 1.3 Overall Design Section 4.1 Overall Design
	
Removal of the reference to "randomized study treatment" in Overall design sections for alignment with CAB program studies and transition to marketed product plan.
	
Transition to marketed product


Section 2.3.1 Risk Assessment
	
Updated section Potential Risk of Clinical Significance: Effects in late stage pregnancy seen in non-clinical studies Summary of Data/Rationale for Risk Animal reproduction studies data updated Mitigation Strategy updated to allow participants who become pregnant to remain in the study.
	
To allow participants who become pregnant to remain in the study

Section 2.3.1 Risk Assessment
	
Added new category: : Potential Risk of Clinical Significance Potential effects in females exposed to dolutegravir during conception and early pregnancy. Summary of Data/Rationale for Risk with data from preliminary analysis of an ongoing birth outcome surveillance study in Botswana involving women exposed to dolutegravir (DTG). Mitigation Strategy updated to allow participants who become pregnant to remain in the study.
	
To allow participants who become pregnant to remain in the study

Section 2.3.1 Risk Assessment
	
Removed text from RPV risks, Rash mitigation strategy: Participants with a Grade 1 or 2 rash will be allowed to continue treatment or to be rechallenged , depending on the clinical judgment of the investigator.
	
Removal of rechallenge option

Section 3 Objectives and Endpoints
	
Added text in bold: Preference for CAB LA + RPV LA every 8 weeks or every 4 weeks compared to daily oral for participants receiving oral bridging during the Maintenance and/or Extension phases will be assessed using a preference questionnaire at Week 152 or Withdrawal
	
Clarification required to be consistent with T&E table: Reason for OB and Preference questionnaire requirements at WD in the extension phase

Section 5.3 Additional Eligibility Criteria
	
Added text: Participation in other interventional studies is generally not permitted, however for eligible participants in South Africa co-enrolment in the AIDS Clinical Trial Group ACTG interventional study (A5392) could be exceptionally permitted after review and approval by Medical Monitor.
	
Co-enrolment in study A5392 would be permitted in South Africa on a case by case approval basis.

Section 5.5 Withdrawal/Stopping Criteria
	
Updated text to clarify the process for participants that discontinue participation when CAB LA + RPV LA is locally available
	
Transition to marketed product

Section # and Name	Description of Change	Brief Rationale
	Removed text: Pregnancy (intrauterine), regardless of termination status of pregnancy.	To allow participants who become pregnant to remain in the study
Section 5.5.1.	Removed "rechallenge" option throughout the sections  Rechallenge option removed throughout all sections New text updated with the current process required in case of restart throughout the section: 
 
- 5.5.1.3 Liver Chemistry Stopping Criteria - Restart
 
- 5.5.1.4 General Guidance Restart
 
- 5.5.1.4.1 Drug Restart
 
 5.5.1.4.2 Drug Restart Following Transient Resolving Liver Events Not Related to IP	Rechallenge option removed
Section 5.6 Participant and Study Completion	Updated text to clarify the Safety Follow up visit requirements	Transition to marketed product
Section 6.10 Discontinuation of Study Treatment	Text added to clarify the process for participants that transition from study treatment to marketed product.	Transition to marketed product
Section 6. Study Treatment	New section added: 6.14 Medical Devices	Medical Device reporting requirement
Section 7.1. Time and Events table	Safety FU visit additional text added to clarify visit requirements	Transition to marketed product
Section 7.1 Time and Events Table	Added new column to list WD assessments during Extension phase Clarification added to the pre-existing WD column to indicate it only refers to WD visit occurred during Maintenance phase  Amended footnotes to clarify requirements for participants who become pregnant during the study  Amended footnotes to clarify the questionnaires required at W152 and WD visit in the Extension phase Withdrawal only if occurring at or prior to Week 152 to Conduct questionnaires/surveys at Withdrawal only if occurring at or prior to Week 152.	To clarify the WD and W152 assessments in the extension phase and add PK testing in case of pregnancy.
Section 7.4.1 Clinical Evaluation	Added text: Participants who are enrolled in the study and have a positive pregnancy test during the course of the study, will be allowed to remain in the study, provided a pregnancy specific ICF addendum is signed by the participant. No IP can be continued (oral or LA) in any pregnant participant until the benefit/risk assessment is discussed with the participant and the pregnancy specific ICF addendum has been signed. See details in Appendix 11. Pregnant participants who remain in the study do not need pregnancy testing during the study, for the duration of their pregnancy.	To allow participants who become pregnant to remain in the study

Section # and Name	Description of Change	Brief Rationale
Section 7.4.3 Adverse Events (AE) and Serious Adverse Events (SAEs)	
Added text throughout Section 7.4.3. and Section 7.4.3.1. referring to the new requirement to report Medical Device incidents.
 
New sections added to cover the new requirement to report Medical Device incidents.
 
7.4.3.9 Medical Device Deficiencies:
 
7.4.3.9.1 Time period for Detecting Medical Device Deficiencies
 
7.4.3.9.2 Follow-up of Medical Device Deficiencies
 
7.4.3.9.3 Prompt Reporting of Medical Device Deficiencies to Sponsor
 
7.4.3.9.4 Regulatory Reporting Requirements for Medical Device Deficiencies
	Added Medical Device incidents reporting requirement
Section 7.4.7 Pregnancy	
Added text throughout all sections below to allow participants who become pregnant to remain in the study:
 
Added text in Section 7.4.7.1
 
Added new Section 7.4.7.2
 
Amended Section 7.4.7.3
 
Amended Section 7.4.7.4
	To allow participants who become pregnant to remain in the study
Section 7.4.7.4 Action to be taken if Pregnancy occurs	Removed text: Additionally, there will be an optional umbilical cord blood collection at time of delivery and/or breast milk after delivery, requiring additional parental informed consent. Cord blood and breast milk samples would be used to better understand the level of PK exposure to the neonate, if any.	Removal of optional umbilical cord blood and/or breast milk pk testing
Section 7.5. Pharmacokinetics	Added text: Pregnant participants will have additional PK samples collected during the duration of the pregnancy.	Added PK collection during pregnancy
Section 7.8.2. Value Evidence and Outcomes endpoints (Exploratory)	
Added text: A preference questionnaire will be administered to participants receiving oral bridging during the Maintenance and/or Extension Phases in order to explore preference for CAB + RPV LA Q4W or Q8W compared to daily oral HIV medication at W152 or upon WD visit if occurred at or before Week 152.
 
Section 7.8.3. Guidance for administering the different versions of HIVTSQc, Preference and Reason for Switch Questionnaires in ATLAS-2M
	Added clarification of Preference questionnaires completion in the extension phase

Section # and Name	Description of Change	Brief Rationale
Section 11.3. Appendix 3	Updated Appendix 3: Liver Safety – Required actions, Follow up Assessments and Study Treatment Restart Guidelines	Removal of rechallenge option
Section 11.5. Appendix 5 Genetics research	Text updated: In the event a participant withdraws from the study and requests destruction of their samples then the site staff must document this in the site study records, complete form F-GRD-001 and must inform ViiV/GSK via the CRA within 5 days of notification by the participant to trigger sample destruction requests.	To align with most recent template requirements
Section 11.7. Appendix 7: Contraceptive Guidance and Collection of Pregnancy Information	Removed footer b of table 14 Highly Effective contraceptive Methods: Two highly effective methods of contraception should be utilized from 30 days prior to the first dose of study medication, throughout the study, and for at least 52 weeks after discontinuation of CAB LA and RPV LA .	Permitted contraceptive methods updated
Section 11.7. Appendix 7: Contraceptive Guidance and Collection of Pregnancy Information	Added text throughout this section for cases of pregnancy during the study	To allow participants who become pregnant to remain in the study
Section 11.8.3. Informed Consent Process	Text added to cover the process for participants that become pregnant and wish to continue in the study. Text added to cover the process for a non-participant that experiences a medical device incident with an AE.	Informed consent process required for pregnant participants who wish to continue participating in the study and non-participants who result injured due to Medical device incident
Section 11.8.7. Data Quality Assurance	Text added (in bold): The sponsor or designee is responsible for the data management of this study including quality checking of the data. Detailed information about study data collection and management process including systems used can be found in the study Data Management Plan.	For clarification purposes
Section 11.10.6.1. Capturing COVID-19 Specific Protocol Deviations	Removed text: Please refer to your study procedure manual for specific details on capturing protocol deviations as a result of COVID-19.	For clarification purposes.
Section 11.11.	New appendix added: Appendix 11: Information and Guidance for Managing Pregnant Participants	To allow participants who become pregnant to remain in the study
Section 11.12.	New appendix added: Appendix 12: Device Deficiencies: Definition and Procedures for	Medical Device reporting requirement

Section # and Name	Description of Change	Brief Rationale
	Recording, Evaluating, Follow-up, and Reporting in Medical Device Studies	
Section 11.13.	Appendix 13: Protocol Amendment history updated	

